### **7.1.7 Blood Hormones/Biomarkers**

Blood samples for measurement of biomarkers i.e. renin and aldosterone will be collected pre-dose and at 3 hours after start of each infusion for Part 1 and renin, aldosterone, norepinephrine, atrial natriuretic peptide, and brain natriuretic peptide will be collected pre-dose and at 3 hours after start of the infusion for Part 2.

The analysis of the biomarkers will be performed at the University of Barcelona, Hospital Clinic.

### **7.1.8 Metabolites in Plasma and Urine**

Metabolites will be analysed in blood collected pre-dose, and at 1, 2, 3, 4, and 6 hours after the start of infusion on Days 1-3 in trial Part 1. In Part 2, blood for analysis of metabolites will be collected pre-dose, 0.5, 1, 2, 3, 4, 5 and at 6 hours after the start of infusion on Day 1.

Blood samples for metabolite pattern will be collected pre-dose and at 3 hours after start of infusion on Day 1 in trial Part 2.

Metabolite analysis will be performed for urine samples taken pre-dose and after each spontaneous void up to 8 hours after start of infusion on Days 1-3 (Part 1) and Day 1 (Part 2).

The analysis of metabolites will be performed under the responsibility of the Bioanalysis Department, Ferring Pharmaceuticals A/S, by means of liquid chromatography coupled mass spectrometry (LC-MS). The analysis will be performed within EU.

### **7.1.9 Pharmacokinetics**

Blood samples for measurement of plasma concentration after the intravenous administration of FE 204205 will be collected pre-dose, and at 0.5, 1, 2, 3, and 4 hours after the start of infusion on Days 1-3 in trial Part 1. The actual sampling time will be recorded in the eCRF.

In Part 2, samples for FE 204205 plasma concentration measurements will be collected pre-dose, and at 0.5, 1, 2, 2.5, 3, 4, and 5 hours after the start of infusion on Day 1. The actual sampling time will be recorded in the eCRF.

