In Part 1, provided that the dose on the preceding day is regarded safe and tolerable, the subsequent dose can be increased. The planned doses for the first 3 patients are 0.01 mg FE 204205 on Day 1, 0.025 mg FE 204205 on Day 2 and 0.05 mg FE 204205 on Day 3. After the SRC has evaluated the preliminary data on safety, tolerability and pharmacodynamics of FE 204205 from the first 3 patients, the planned doses for the remaining 3 subjects may be increased to maximum 0.025 mg FE 204205 on Day 1, 0.05 mg FE 204205 on Day 2 and 0.1 mg FE 204205 on Day 3 (see protocol section 3.4). Dose escalation in the subject on Days 2 and 3 will only commence provided that the increase in mean arterial pressure from baseline is  $< 15$  mmHg, absolute mean arterial pressure  $\leq 120$  mmHg, systolic blood pressure  $\leq 160$  mmHg, diastolic blood pressure  $\leq 100$  mmHg, and heart rate  $\geq 55$  beats per minute at all of the vital signs assessments during the 4 hours after start of infusion on the previous day. If these criteria are not met, the same dose will be administered the next day. If the increase of dose results in non-tolerable effects, the preceding tolerated dose will be reverted to for the remaining administration in that subject. The highest planned dose of 0.1 mg infused over 2 hours ( $= 0.05$  mg/hr) corresponds to the infusion rate applied for the dose level of 0.3 mg IV infused over 6 hours ( $= 0.05$  mg/hr) given to healthy subjects and is expected to not exceed the exposure in healthy subjects by means of  $C_{max}$  (expected  $C_{max}$ : approximately 3 ng/mL). At this dose level in healthy subjects (0.05 mg/hr IV over 6 hours), the mean arterial pressure increased (max. mean increase of +14 mmHg) and the pulse decreased. The dose level was safe and well tolerated in healthy subjects, as were dose levels up to 3 times higher (highest dose level studied in healthy subjects was 0.9 mg infused over 6 hours = 0.15 mg/hr).

The highest planned dose of 0.1 mg infused over 2 hours ( $= 0.05$  mg/hr) that may be reached on Day 3 is the same that was assigned to patient █ on Day 1. However, this dose level will only be reached in a patient in Part 1 who has already tolerated two lower dose levels of FE 204205 on Day 1 and Day 2 and met the dose escalation criteria above.

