## 7 TRIAL ASSESSMENTS

### 7.1 Assessments Related to Endpoints

Actual sampling times for assessments will be recorded in the eCRF.

In the event that the infusion is stopped prior to two hours after start, all subsequent assessments related to endpoints should be performed as if the infusion stopped at 2 hours, i.e. PK sampling in Part 1 at infusion stop and 1 and 2 hours after stop, vital signs in Part 1 at infusion stop and 0.25, 0.5, 1, 2, and 4 hours after stop, etc.

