#### Treatment Emergent Adverse Event

A treatment emergent adverse event is any AE occurring after the administration of the IMP and within the time of residual drug effect, or a pre-treatment adverse event or pre-existing medical condition that worsens in intensity after administration of the IMP and within the time of residual drug effect.

The time of residual drug effect is the estimated period of time after the administration of the IMP, where the effect of the product is still considered to be present based on pharmacokinetic (PK), pharmacodynamic (PD) or other substance characteristics. The residual drug effect is generally accepted to be 5 times the terminal half-life. The terminal half-life of FE 204205 is anticipated to be within the range of 3 hours, i.e. in this study the residual drug effect is likely to be well within the time to the last assessment in both Part 1 and Part 2. Since this is the first time FE 204205 is administered to patients with cirrhotic portal hypertension, all AEs occurring from start of infusion on Day 1 up to the last assessment on Day 4 in Part 1 and Day 2 in Part 2 are regarded as treatment emergent.

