#### **9.6.2.8 Pharmacokinetics**

The pharmacokinetic analysis will be based on the PP analysis set and performed by Department of Experimental Medicine, Ferring Pharmaceuticals A/S. The pharmacokinetic parameters will be calculated by non-compartmental analysis (NCA) using the software Phoenix WinNonlin® (Pharsight Corporation, U.S.A.). Actual sampling time points relative to dosing (i.e. starting time of dose infusion) will be used for the NCA and on the individual plots of plasma concentration versus time. Scheduled time points will be used in the descriptive summaries and summary plots of the data. Plasma concentration values below lower limit of quantification (LLOQ) and missing values (e.g. no blood sample collected or no value obtained at analysis) will be excluded from the NCA. Values below LLOQ will be represented by ‘LLOQ/2 in summary tables and plots of the data. No formal analysis of “outliers” is planned.

From the plasma and urine concentration-time data of FE 204205 the following parameters will be estimated, if possible: AUC, AUCt, % Extrap AUC, Cmax, tmax, CL, Vz, λz, t1/2, MRT, Ae and CLR.

Selection of data points for calculation of  $t_{1/2}$  via  $\lambda_z$  will be based on the following considerations:

- AUC will be calculated by the linear trapezoidal method
- The automatic range selection used in Phoenix WinNonlin® will be used to propose an optimal number of time points to use for the calculation of  $\lambda_z$ .
- At least three samples above LLOQ obtained during the log-linear elimination phase will be included in the calculation of the  $\lambda_z$ .
- The final selection of samples for calculation of  $\lambda_z$  will be based on visual inspection of log concentration-time plots of individual profiles.

Pharmacokinetic parameters will be presented by treatment (only for subjects receiving active treatment) with number of measurements, number of missing data, mean, standard deviation, median, minimum, maximum, geometric mean, and %CV (based on untransformed data) for geometric mean (for AUC and  $C_{max}$ ). For  $t_{1/2}$ , the harmonic mean will be listed instead of the geometric mean. For  $t_{max}$  the geometric mean and the CV% will be omitted.

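### The PK set drops patients with measured baseline HVPG below 12 mmHg, Part 1 plasma sampling gives only the minimum three points for λz, and metabolite draw times conflict at two time points in each part

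*Combined protocol and SAP*

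**What the plan says.** **PK analysis set.** The Synopsis, Section 9.4.2 and Section 9.6.2.8 all place the PK analysis on the per protocol (PP) set. Section 9.4.2 limits that set to dosed patients who have no major deviation and whose baseline HVPG is at least 12 mmHg. It also lets subjects be left out where a PK parameter is too imprecise, with criteria deferred to the SAP. Inclusion criterion 3 asks only for an HVPG anticipated from history. In Part 1, HVPG is first measured before dosing on Day 3 (Table 6-1, footnote 8).

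**Parent-drug sampling.** Section 7.1.9 has Part 1 plasma "collected pre-dose, and at 0.5, 1, 2, 3, and 4 hours after the start of infusion on Days 1-3 in trial Part 1". Part 2 adds 2.5 h and 5 h. For an infusion stopped early, Section 7.1 describes "PK sampling in Part 1 at infusion stop and 1 and 2 hours after stop". Section 8.1 states: "The terminal half-life of FE 204205 is anticipated to be within the range of 3 hours".

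**Estimation rule.** Section 9.6.2.8 says "At least three samples above LLOQ obtained during the log-linear elimination phase will be included in the calculation of the" terminal rate constant λz. The final choice of points "will be based on visual inspection of log concentration-time plots of individual profiles". Values below LLOQ are left out of the non-compartmental analysis, and "the following parameters will be estimated, if possible".

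**Metabolite sampling.** For Part 1, Section 7.1.8 states: "Metabolites will be analysed in blood collected pre-dose, and at 1, 2, 3, 4, and 6 hours after the start of infusion". For Part 2 it lists pre-dose, 0.5, 1, 2, 3, 4, 5 and 6 h. Footnote 5 of Tables 6-1 and 6-2 covers parent drug and metabolites together and gives different lists.

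**The concern.** Pharmacokinetics is a stated objective, and this is the first study of FE 204205 in these patients. Three features work against that objective.

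- A portal-pressure threshold decides whose concentrations are analysed. A patient can enter on an anticipated value, provide valid profiles, and then be dropped because the measured value is lower. In Part 1 the Day 1 and Day 2 profiles already exist when HVPG is first measured. A Part 1 patient with no Day 3 catheterization has no HVPG with which to qualify.
- Part 1 is the only part that spans the 0.01 to 0.1 mg range, and its schedule has no spare point for λz.
- The site is given two metabolite schedules and cannot follow both.

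**Working it through.** The plan states no precision for λz and no expected extrapolated share, so there is no figure of its own to reproduce.

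**1. Profiles lost through the PK set**

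Table 5-1 gives 6 patients × 3 days = 18 planned Part 1 profiles. By dose, if escalation goes as planned: 0.01 mg, 3; 0.025 mg, 3 + 3 = 6; 0.05 mg, 3 + 3 = 6; 0.1 mg, 3. One patient below 12 mmHg removes 3 of 18: one of 3 at the lowest or highest dose, and one of 6 at each middle dose. No HVPG minimum is set for Part 1.

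In Part 2, Section 3.2 targets at least 18 of about 20 patients at or above 12 mmHg, which allows 20 − 18 = 2 below. Only patients on active drug contribute profiles, so the loss is 0 to 2 of 16.

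**2. Points available for λz**

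Part 1 samples from infusion stop onward: 2, 3 and 4 h, so three against a minimum of three. All three must be above LLOQ, and the infusion-stop sample must be log-linear. Part 2 has five (2, 2.5, 3, 4, 5 h), or four without the infusion-stop sample.

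**3. Precision when all three points are usable**

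Assumptions, because the documents give neither: mono-exponential decline, and a 10% concentration error (e = 0.10). With k = ln 2 / t1/2 and last sample at T hours:

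- share of AUC extrapolated = (1 − exp(−2k)) × exp(−k(T − 2)) / (2k)
- CV of λz = e / (k × √Σ(t − t̄)²)

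For t1/2 3 h, k = 0.231. The extrapolated share at 4 h is 0.370 × 0.630 / 0.462 = 0.504. For 2, 3, 4 h, Σ(t − t̄)² = 2, so the CV is 0.10 / (0.231 × 1.414) = 30.6%. For 2, 3, 4, 6 h, Σ(t − t̄)² = 8.75, so the CV is 14.6%.

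| t1/2 | Extrapolated, last sample 4 h (Part 1) | 5 h (Part 2) | 6 h | λz CV, 2, 3, 4 h | λz CV, 2, 3, 4, 6 h |
|---|---|---|---|---|---|
| 1 h | 13.5% | 6.8% | 3.4% | 10.2% | 4.9% |
| 2 h | 36.1% | 25.5% | 18.0% | 20.4% | 9.8% |
| 3 h | 50.4% | 40.0% | 31.8% | 30.6% | 14.6% |
| 4 h | 59.8% | 50.3% | 42.3% | 40.8% | 19.5% |

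At 5% error the CVs halve (15.3% and 7.3% at t1/2 3 h). If the infusion-stop sample is not log-linear, adding 6 h still leaves 3, 4 and 6 h, with a CV of 20.0% at t1/2 3 h and 10% error. Without it, two points remain and the rule gives no λz.

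**4. Would a 6 h sample be measurable?**

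Section 3.5.4 says the top dose "is expected to not exceed the exposure in healthy subjects by means of" Cmax and gives about 3 ng/mL. That figure can refer to the 6 h infusion in healthy subjects or to the 2 h infusion here. On the first reading, the 2 h peak at t1/2 3 h is 3 × (1 − exp(−2k)) / (1 − exp(−6k)) = 1.48 ng/mL. On the second it is 3 ng/mL. Multiplying by exp(−4k) gives the 6 h level, and 0.01 mg is scaled linearly from 0.1 mg.

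| t1/2 | 0.1 mg | 0.01 mg |
|---|---|---|
| 3 h | 0.59 or 1.2 ng/mL | 0.06 or 0.12 ng/mL |
| 1 h | 0.14 or 0.19 ng/mL | 0.014 or 0.019 ng/mL |

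The LLOQ is not stated.

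**5. Metabolite times side by side (hours after start, pre-dose in all)**

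| | Section 7.1.8 | Footnote 5 | Differ at |
|---|---|---|---|
| Part 1 | 1, 2, 3, 4, 6 | 0.5, 1, 2, 3, 4 | 0.5 and 6 |
| Part 2 | 0.5, 1, 2, 3, 4, 5, 6 | 0.5, 1, 2, 2.5, 3, 4, 5 | 2.5 and 6 |

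The parent-drug times agree between Section 7.1.9 and the footnotes.

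**The case against.** The plan accepts limits on its PK estimates. Parameters are estimated only where possible, and imprecise ones may be excluded, so the likely Part 1 outcome is a missing estimate rather than a wrong one. Part 2 is better sampled. Section 3.5.1 frames Part 1 around safety, tolerability and pharmacodynamics, and the listed basis for dose selection contains no PK. No dose-proportionality analysis is planned. This stands, and it limits the weight of the sampling point. It does not remove the point, because these rules deal with failed estimates only after they occur, and Part 2 studies one dose.

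The half-life wording can mean about 3 h or up to 3 h. That is also fair, which is why a range is shown.

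Restricting analysis to the target population is defensible for pharmacodynamics. The documents give no PK reason for it.

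A reader might infer that Part 1 half-lives will be underestimated. That would need a distribution phase and acceptance of the three-point fit despite it. The documents do not give the curve shape, and visual inspection may catch the problem, so this carries no weight here. A reader might also infer that the metabolite schedule is undefined. It is not: pre-dose, 1, 2, 3 and 4 h agree in both parts, as do 0.5 and 5 h in Part 2.

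**Conclusion.** The concern holds in three limited parts.

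- **PK set:** valid profiles can be dropped for a non-PK reason. The loss is 3 of 18 planned Part 1 profiles per affected patient, and 0 to 2 of 16 active patients in Part 2 under the recruitment target. How likely a low measured HVPG is cannot be judged from the documents.
- **Part 1 sampling:** three points against a minimum of three, so losing one removes λz and every parameter that depends on it for that profile. With all three, extrapolated AUC is 14% to 60% for t1/2 1 to 4 h (50% at 3 h), and the λz CV at 3 h is 31%. A 6 h sample gives 3% to 42% (32% at 3 h) and a CV of 15%, so it reduces the problem without removing it. These figures rest on mono-exponential decline and, for the CVs, an assumed 10% error.
- **Metabolite times:** a plain contradiction at 0.5 and 6 h in Part 1 and at 2.5 and 6 h in Part 2.

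A reader might take this to undermine safety evaluation or the choice of Part 2 dose. The documents do not support that: Cmax, tmax and AUCt do not depend on λz, and dose selection rests on safety and haemodynamic data.

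**What to change.** 1. Define the PK set as all patients given FE 204205 with evaluable concentrations, without the HVPG criterion. Apply the precision exclusion parameter by parameter. This is a wording change in the Synopsis and Sections 9.4.2 and 9.6.2.8.
2. Assay FE 204205 at 6 h in both parts, using the safety blood draw already scheduled then (footnote 1 of Tables 6-1 and 6-2). Align the early-stop sampling rule in Section 7.1 with the new schedule. The cost is 6 × 3 + 16 = 34 assays (6 × 3 + 20 = 38 if placebo samples are assayed) and a small extra tube volume while patients are still resident. The downside is that the 6 h level may fall below the LLOQ at low doses, most of all at 0.01 mg (3 of 18 profiles).
3. Reconcile Sections 7.1, 7.1.8 and 7.1.9 and footnote 5 of both flow charts to one blood-sampling list, stating which metabolite times are intended. This is wording only.

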### **7.1.10 Systemic Haemodynamics**

In Part 1 will systemic haemodynamics be assessed by measuring blood pressure and heart rate with non-invasive methods at screening, on Day -1, pre-dose and, 0.25, 0.5, 1, 1.5, 2, 3, 4, and 6 hours after start of infusion on Days 1-3, and in the morning of Day 4 as well as at the follow-up visit (see Section 7.1.2). In addition, PCWP, PAP, RAP, MAP and CO will be measured by a Swan-Ganz catheter introduced into the pulmonary artery pre-dose, and 2 hours after start of infusion on Day 3. CO, MAP, and RAP will be used for calculation of SVR.

In Part 2, blood pressure and heart rate will be measured with non-invasive methods at screening, on Day -1, pre-dose and, 0.25, 0.5, 1, 1.5, 2, 3, 4, and 6 hours after start of infusion on Day 1, and in the morning of Day 2 as well as at the follow-up visit (see Section 7.1.2). In addition, PCWP,

PAP, RAP, MAP and CO will be measured by a Swan-Ganz catheter introduced into the pulmonary artery pre-dose, and 2 hours after start of infusion on Day 1. CO, MAP, and RAP will be used for calculation of SVR.

### **7.1.11 Portal Haemodynamics**

Measurements of portal haemodynamics to assess FHVP, WHVP, and IVC will be performed by hepatic vein catheterization pre-dose and at 1 and 2 hours after start of infusion on Day 3 in Part 1 and on Day 1 in Part 2. IVC will be measured pre-dose and at 2 hours after start of infusion only.

All measurements will be performed at least in duplicate (the average will be used for the endpoint), and permanent tracing will be obtained with a multichannel recorder and adequately calibrated transducers. The HVPG is calculated as the difference between the WHVP and FHVP.

Measurement of HVPG is a safe procedure and is used routinely in clinical practice in patients with chronic liver failure.

### **7.1.12 Body weight**

Body weight for the assessment of any effect on possible ascites will be performed in Part 1 predose on Days 1-3 and in the morning on Day 4. In Part 2 it will be performed predose and in the morning on Day 2.

## **7.2 Other Assessments**

### **7.2.1 Demographic and Baseline Data**

Information about gender, date of birth, body weight, height, BMI, and medical history will be collected at the screening visit for each subject.

### **7.2.2 Physical Examinations**

A physical examination will be performed at screening, to determine eligibility, and at the follow-up visit for both Part 1 and Part 2. The full physical examination comprises examination of general appearance, central and peripheral nervous system, head and neck (including ears, eyes, nose, mouth and throat), cardiovascular system, respiratory system, gastrointestinal system, lymphatic system, urinary system, skin and musculoskeletal system.

### **7.2.3 Serology**

Determination of HIV-1 and HIV-2 antibodies, hepatitis B surface-antigen, and hepatitis C virus antibodies will be performed at screening for eligibility purposes.

### **7.2.4 Drug Screen and Alcohol Urine Test**

To ensure that drugs are not abused, a urine dip-stick drug screen and an alcohol urine test will be performed at screening, and on Day -1 in both Part 1 and Part 2.

The drug screening will be performed from fresh mid-stream urine for the determination of amphetamines, benzodiazepines, cannabinoids, cocaine, ecstasy, opiates, and methadone.

### **7.2.5      Pregnancy Test**

In women, serum  $\beta$ -hCG will be determined at screening, on Day -1 and at follow-up in both Part 1 and Part 2, using validated standard methods.

### **7.2.6      Prior and Concomitant Medication**

Information about prior and concomitant medication will be collected for each subject throughout the study.

### **7.3      Drug Concentration Measurements**

Analysis of plasma and urine concentrations of FE 204205, metabolite concentrations, and metabolite patterns will be performed under the responsibility of the Department of Bioanalysis at Ferring Pharmaceuticals A/S by means of a validated tandem mass spectrometry based (LC-MS/MS) method. The analysis will be performed within EU.

### **7.4      Handling of Biological Samples**

A detailed description of all sample collections and shipment procedures will be included in a separate laboratory manual. The Sponsor or third party(ies) will store the blood samples up to 2 years after reporting of the trial.

## 8 ADVERSE EVENTS

### 8.1 Adverse Event Definition

An adverse event is any untoward medical occurrence in a subject participating in a clinical trial. It includes:

- Any unfavourable and unintended sign, symptom or disease temporally associated with the use of the IMP, whether or not considered to be caused by the IMP.
- Adverse events commonly observed and adverse events anticipated based on the pharmacological effect of the IMP.
- Any laboratory abnormality, vital sign or finding from physical examination assessed as clinically significant by the Investigator [note: pre-existing conditions diagnosed through assessments and examinations at the screening visit or during the screening period are not adverse events, but are recorded as medical history.]
- Accidental injuries, reasons for any change in medication (drug and/or dose), reasons for any medical, nursing or pharmacy consultation, or reasons for admission to hospital or surgical procedures.
- Overdoses and medication errors with and without clinical consequences.

#### Pre-treatment Adverse Event

A pre-treatment adverse event is any untoward medical occurrence arising or observed between signing of informed consent and the first administration of the IMP.

#### Treatment Emergent Adverse Event

A treatment emergent adverse event is any AE occurring after the administration of the IMP and within the time of residual drug effect, or a pre-treatment adverse event or pre-existing medical condition that worsens in intensity after administration of the IMP and within the time of residual drug effect.

The time of residual drug effect is the estimated period of time after the administration of the IMP, where the effect of the product is still considered to be present based on pharmacokinetic (PK), pharmacodynamic (PD) or other substance characteristics. The residual drug effect is generally accepted to be 5 times the terminal half-life. The terminal half-life of FE 204205 is anticipated to be within the range of 3 hours, i.e. in this study the residual drug effect is likely to be well within the time to the last assessment in both Part 1 and Part 2. Since this is the first time FE 204205 is administered to patients with cirrhotic portal hypertension, all AEs occurring from start of infusion on Day 1 up to the last assessment on Day 4 in Part 1 and Day 2 in Part 2 are regarded as treatment emergent.

